9.2. Exposure and Compliance

The duration of study drug exposure is defined as the number of days on treatment from the first dose of study drug until the last dose of study drug (last dose–first dose+1), excluding the off-treatment period between the Week 48 visit and Week 52 visit prior to protocol version 6. Study drug exposure is summarized by descriptive statistics. Summaries include the total dose (mg) received (based on the number of pills returned), study drug compliance (including the number of patients with $\geq 80\%$ compliance through Week 100, duration (days) of exposure during the study treatment period, and the number and percentage of patients who reached the goal at any point during the study. The overall treatment duration for all placebo patients and bardoxolone methyl patients who completed treatment through Week 100 vs. bardoxolone methyl patients who did not complete treatment through Week 100 is also summarized. In addition, a summary of the number and percentage of patients exposed by dose (placebo, 5 mg, 10 mg, 20 mg, 30 mg) and by visit is generated. If a patient received more than 1 dose during a visit window, the duration of the longest constant dose is used to calculate exposure. A summary of the number and percentage of patients exposed to study drug by treatment will be summarized for the following duration categories:

- ≤ 16 Weeks
- >16 Weeks
- >24 Weeks
- >48 Weeks
- >72 Weeks
- >96 Weeks

Total number of doses dispensed, and total dose (mg) dispensed is calculated from total number of kits (bottles) recorded on the Study Drug Dispensation electronic case report form (eCRF). Total number of doses received is calculated from information on the eCRF of Study Drug Return and Study Drug Dispensation, as the (total number of doses dispensed – total number of doses returned). If a kit is not returned but the patient had a subsequent dispensation, then the non-returned kit is assumed to have been taken in full. However, if a kit is not returned and no kit is subsequently dispensed, then the non-returned kit is assumed to not have been taken. Study drug compliance (%) is calculated as $100 \times \text{total number of doses received} / \text{total number of}$

study days of study participation, excluding the off-treatment periods between Week 48 to Week 52 prior to protocol version 6 and Week 100 to Week 104.

The off-treatment periods between Week 48 to Week 52 prior to protocol version 6 and Week 100 to Week 104 will be analyzed by the summary of days since last dose. Indeed, for patients with a Week 52 off-treatment analysis visit, summary statistics of days since last dose are generated. Similarly, for patients with a Week 104 analysis visit, summary statistics of days since last dose are generated.

The number and percentage of patients are summarized by treatment group for Drug Interruption not related to COVID-19:

- Interruption Type (Primary Investigator (PI) initiated, Patient Reported)
- Primary reason for interruption (AE, Elevated Transaminase not clinically significant (NCS), Elevated BNP NCS, Fluid Overload NCS, Weight Gain NCS, Weight Loss NCS, Other)

Drug Interruption due to COVID-19 will also be summarized as specified in Section 11.1.

Patients not at per-protocol dose are listed, including reasons.

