#### **8.3.2. Treatment Period**

The Treatment Period refers to the time from administration of the first dose (Day 1 visit) through administration of the last dose (Week 100 visit). Administration of the first dose of study drug should occur in-clinic, at the Day 1 visit, after confirmation of eligibility and

randomization. Administration of the last dose of study drug should occur in-clinic, at the Week 100 visit, following the collection of all lab and PK assessments.

During the treatment period, sites should ensure proper documentation of any intentional interruptions in dosing, including the reason for and duration of the interruption. Information regarding interruptions should be entered into the clinical database.

A patient who discontinues study drug early has a shortened treatment period. Regardless of when a patient's treatment period ends, it is imperative that an off-treatment period follows study drug discontinuation. See Section 8.3.3 for required assessments in the Off-Treatment Period.

If a patient resumes study drug, the patient should resume the normal study schedule and follow instructions in Section 9.11 regarding dose interruption and re-challenge.

All assessments during the Treatment Period should occur per the Schedule of Assessments, in Table 4.

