**9.10.13. Study Drug Administration**

For dose levels up to 20 mg, patients should self-administer one capsule orally once a day beginning on Day 1 (in clinic) through the end of the Treatment Period, as indicated in Table 4. Patients who dose escalate to 30 mg should administer two capsules orally once a day. Each dose of study drug should be administered at approximately the same time each day. Study drug administration should be recorded in a patient diary through Week 100.

A vomited dose must not be replaced. A double dose (e.g., missed dose from previous day and dose for current day) must not be taken.

Refer to Section 9.4 and 9.11 for treatment compliance and detail in dose management.

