**9.10.14. Study Drug Dispensation and Collection**

Study drug will be dispensed to the patient and collected from the patient as indicated in Table 4. The patient will be dispensed the appropriate number of treatment kits at each timepoint: Day 1, Week 2, Week 4, Week 6, Week 8, Week 12, Week 24, Week 36, Week 48, Week 52 (B), Week 64, Week 76, and Week 88. If the patient is provided more than one kit, only one treatment kit should be opened at a time. Dispensed treatment kits from each visit (including unscheduled visits) should be returned to the site for collection as indicated in Table 4 or at the subsequent visit.

If the appropriate number of treatment kits (e.g., a 3-month supply) cannot be dispensed as outlined in Table 4, a partial supply may be provided to the patient. The remainder may be provided separately to the patient. Every effort should be made to avoid interruptions in dosing.

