### 10.2. Study Drug Packaging and Labeling

The study drug will be supplied as either individual bottles (5, 10, 20 mg dose) or in tamper-evident kits containing two high-density polyethylene (HDPE) bottles (30 mg dose as 2 x 15 mg capsules). Each bottle will utilize foil induction-seal liners and a child-resistant closure. Each bottle of study drug will contain 30 capsules of 5 mg, 10 mg, 15 mg, or 20 mg strength bardoxolone methyl or the matching placebo capsules. Each bottle will also contain desiccant insert(s) that must not be ingested. Labeling on each kit bottle will contain at minimum the following information:

- Medication ID number;
- Protocol 402-C-1808;
- Caution Statement: New Drug – Limited by Federal Law to Investigational Use. Keep out of reach of children;
- Control or lot number;
- Store at 15° – 25°C (59° – 77°F);
- Reata Pharmaceuticals, Inc., Irving, TX.

When applicable, a double-panel label will be presented on the treatment kit carton containing this and other information. Additionally, labeling, in the relevant local languages for study drug use and distribution in the EU shall adhere to current Eudralex, Volume 4 Annex 13 guidance and requirements.

In the event the investigational product is not packaged as intended or may not adhere to Current Good Manufacturing Practices (CGMP), a complaint should be filed with the Sponsor, ideally through the site's CRA. Guidance on filing study drug complaints is available in the Study Reference Manual, and attention should be given to ensure the patient number is not submitted within the complaint documentation.

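### SAP 9.2 credits an unreturned kit as all or nothing, ignoring recorded last-dose dates and interruptions, so total dose and the compliance numerator can be wrong in either direction for patients with missing kits

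*SAP*

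**What the plan says.** SAP 9.2 (Exposure and Compliance) takes the dose count from drug-accountability forms alone: "Total number of doses received is calculated from information on the eCRF of Study Drug Return and Study Drug Dispensation", as dispensed minus returned. Missing kits are handled by two sentences. The first is "If a kit is not returned but the patient had a subsequent dispensation, then the non-returned kit is assumed to have been taken in full". The second covers the opposite case: "if a kit is not returned and no kit is subsequently dispensed, then the non-returned kit is assumed to not have been taken". Total dose received (mg), compliance, and the number of patients with at least 80% compliance all rest on this count. No sensitivity rule is given.

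The same section measures duration from dates: "The duration of study drug exposure is defined as the number of days on treatment from the first dose of study drug until the last".

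Protocol 8.3.2 asks sites to document the reason for and length of intentional interruptions and adds: "Information regarding interruptions should be entered into the clinical database". On supply, Protocol 10.2 says "Each bottle of study drug will contain 30 capsules of 5 mg, 10 mg, 15 mg, or 20 mg strength", and Protocol 9.10.13 says that up to 20 mg "patients should self-administer one capsule orally once a day". Protocol 9.10.14 lists the dispensing visits as "Day 1, Week 2, Week 4, Week 6, Week 8, Week 12, Week 24, Week 36, Week 48, Week 52 (B), Week 64", then Weeks 76 and 88. Nothing is dispensed at Week 100, where Protocol 8.3.2 places the last dose in clinic.

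**The concern.** The rule infers intake from whether a bottle came back. Bottle return and capsule intake are different things, and the database should hold better evidence on intake in the form of first- and last-dose dates and recorded interruptions.

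The titration bottles hold about twice what is needed before the next visit, so crediting a missing one in full gives a dose count that once-daily dosing cannot produce. Crediting the last supply as zero can contradict a last-dose date on the same patient's record. The report could then show a patient with exposure days running to Week 100 and no doses for the final stretch, or a patient with a tabulated interruption and full credit for the same weeks.

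At stake is how well the exposure tables describe drug delivery for the affected patients. The zero branch may matter more than usual here. SAP section 2 reports that the decision to discontinue development went to all sites on 10 May 2023, and any patient on drug then had a final supply with no later dispensation.

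**Working it through.** The plan gives no dose or compliance figure to reproduce, so the check applies the SAP rule to the protocol's own schedule.

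**Inputs**
- Doses per kit: 30 (Protocol 10.2). The 30 mg kit is two bottles of 15 mg capsules taken two a day, so it also holds 30 doses.
- Dosing: once daily (Protocol 9.10.13).
- Scheduled intervals from the dispensing visits: four of 14 days (Day 1 to Week 8), one of 28 (Weeks 8 to 12), three of 84 (Weeks 12 to 48), one of 28 (Weeks 48 to 52), four of 84 (Weeks 52 to 100). Total: 4×14 + 28 + 3×84 + 28 + 4×84 = 700 days.
- Kits per 84-day interval: three. This is an assumption, being the fewest 30-dose kits that cover 84 days. It fits the 3-month supply mentioned in Protocol 9.10.14.
- Number of missing kits: not stated anywhere.

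**Over-credit (missing kit, later dispensation)**
- One titration bottle: credited 30, possible 14, excess 30 − 14 = 16 doses. All four: 4×16 = 64. Visit windows do not close the gap: with ±3 days at both ends the interval is at most 14 + 3 + 3 = 20 days.
- One 84-day supply: credited 3×30 = 90. With no interruption, 84 doses are possible (excess 6). With a recorded 28-day interruption, 84 − 28 = 56 (excess 34). With a recorded 56-day interruption, 84 − 56 = 28 (excess 62). The credit is 90 in every case.

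**Under-credit (missing kit, no later dispensation)**
- Whole Week 88 supply missing, recorded last dose at Week 100: credited 0, possible 700 − 616 = 84. At 20 mg that removes 84×20 = 1,680 mg from total dose.
- Part of that supply missing: suppose the open kit comes back with 6 doses left (24 taken) and two empty kits do not. The credit is 24 and 2×30 = 60 doses are lost.

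**Same-section conflict**
In the first under-credit case, exposure duration counts all 700 treatment days while doses received stop at 616.

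**Rule bounded by recorded dates**
For each dispensing visit let D = days to the earlier of the next dispensation or last dose, minus interruption days. Credit for the missing kits = min(missing content, max(0, D − doses accounted for by returned kits)).

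| Case | SAP 9.2 | Bounded rule |
|---|---|---|
| Titration bottle missing | 30 | min(30, 14) = 14 |
| 84-day supply missing, 56 days interrupted | 90 | min(90, 28) = 28 |
| Week 88 supply missing, dosed to Week 100 | 0 | min(90, 84) = 84 |
| Week 88: one kit back with 24 taken, two missing | 0 for the two | min(60, 84 − 24) = 60 |

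The cap has to act on the whole supply. If each of three kits were capped separately in the second case, the result would be 3×28 = 84 doses for 28 dosing days.

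**The case against.** The strongest reply is that little depends on this. Protocol 9.4 and 10.5 ask for every bottle back, and Table 4 schedules collection at each dispensing visit from Week 2 and at Week 100, so missing kits may be few. A completer takes the final dose in clinic at Week 100 and would probably bring at least the open kit, so losing the whole Week 88 supply is a worst case. Exposure duration uses dates and is unaffected. Interruptions are tabulated by type and reason in SAP 9.2 and 11.1. The SAP has no per-protocol set, and its primary and secondary efficacy analyses use neither dose nor compliance. The zero branch is right if nothing was taken, and it agrees with SAP 6.6.4, which sets an incomplete end-of-treatment date to the last dispensation date. All of this stands. It limits the size of the point but does not make the rule agree with recorded dates.

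A reader might infer more than the documents support:
- **That compliance is wrong across the trial, or biased between arms.** Only patients with missing kits are affected, and neither their number nor their split by arm is given. More interruptions on active drug would not be enough; interrupted patients would also have to keep their kits. Protocol 5.1.2.2 says most transaminase elevations resolved while dosing continued.
- **That the rule pushes fully adherent patients below 80%.** Dividing by treatment days suggests this: a patient who stops on Day 161 with the Week 12 supply missing would read 84/161 = 52%. But SAP 9.2 divides by days of study participation, less Weeks 48 to 52 before protocol version 6 and Weeks 100 to 104. Taken literally, for a patient treated wholly under version 6 or later and followed to Week 112, that is 784 − 28 = 756 days. Even with every dose counted the result is 161/756 = 21%. The denominator is a separate issue.
- **That the report will show 214% compliance (30/14).** SAP compliance is a whole-study figure, and no interval value is planned.

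**Conclusion.** The point holds for patients with unreturned kits. For them, SAP 9.2 can overstate total dose received and the compliance numerator by 16 doses per titration bottle, and by 62 doses for an 84-day supply with a recorded 56-day interruption. It can understate them by up to 84 doses for the last supply, against the exposure duration in the same section. The titration figure follows from bottle content, once-daily dosing and the visit schedule. The 84-day over-credit also assumes three kits per interval.

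The consequence is confined to descriptive exposure and compliance summaries. The trial-level size and net direction cannot be determined from the documents, and the effect of the May 2023 stop is an inference, not a count. The change is worth making because the rule overrides better data already collected, but it does not threaten the efficacy conclusions.

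**What to change.** Replace both missing-kit sentences in SAP 9.2 with one rule applied to the whole supply dispensed at a visit, all kits together:

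- Doses taken from that supply cannot exceed the days from its dispensation to the earlier of the next dispensation or the recorded last dose, minus recorded interruption days. The planned Week 48 to 52 withdrawal before protocol version 6, which SAP 9.2 already excludes from exposure, counts as non-dosing days.
- Credit the unreturned kits with that number less the doses accounted for by returned kits, not below zero and not above the unreturned content.
- If the last-dose date is incomplete, SAP 6.6.4 applies, and the final supply is then credited as zero, as now.
- State the day-counting convention, label the result an upper bound because it assumes daily dosing between recorded dates, and report the number of imputed kits by arm.

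The cost is a short extra derivation from dates the database should already hold. Some reported compliance values will fall, and missed doses that were not recorded as interruptions will still be hidden in unreturned kits.

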## 7. INVESTIGATIONAL PLAN

### 7.1. Overall Study Design

This international, multi-center, randomized, double-blind, placebo-controlled phase 3 trial will study the safety, tolerability, and efficacy of bardoxolone methyl in qualified patients with ADPKD. Approximately 850 patients will be enrolled.

Patients will be randomized 1:1 to either bardoxolone methyl or placebo. Randomization will be stratified by eligibility eGFR category (30 to <60;  $\geq$ 60 to 90), concomitant tolvaptan use (yes, no), and screening ACR ( $\leq$ 300 mg/g, >300 mg/g). Patients randomized to placebo will remain on placebo throughout the study, undergoing sham titration. Patients with eGFR 60 to 90 mL/min/1.73 m^2 at screening should not comprise more than approximately 40% of enrolled patients.

The maximum bardoxolone methyl dose will be determined by baseline proteinuria status. Patients with baseline ACR  $\leq$  300 mg/g will be titrated to a maximum dose of 20 mg, and patients with baseline ACR > 300 mg/g will be titrated to a maximum dose of 30 mg. Patients receiving bardoxolone methyl will start with once-daily dosing at 5 mg and will dose-escalate to 10 mg at Week 2, to 20 mg at Week 4, and then to 30 mg at Week 6 (only if baseline ACR > 300 mg/g) unless contraindicated clinically and approved by the Medical Monitor. Dose de-escalation is permitted during the study if indicated clinically, and subsequent dose re-escalation is also permitted to meet the dosing objective of the highest tolerated dose.

All patients in the study will follow the same visit and assessment schedule. Following randomization on Day 1, patients will be scheduled to be assessed during treatment at Weeks 1, 2, 4, 6, 8, 12, 24, 36, 48, 52, 64, 76, 88, and 100 and by telephone contact on Days 3, 10, 21, 31, 38, and 45. Patients will continue study drug treatment through Week 100. Patients will also be scheduled to be assessed at an in-person follow-up visit at Weeks 103, 104, 108, and 112 after the end of treatment, respectively.

Efficacy endpoints will be analyzed after all enrolled patients have completed the study and the database has been locked. All enrolled patients are expected to remain on their blinded treatment assignment through Week 100, and to complete all scheduled assessments through Week 112.

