### 8.3.3. Off-Treatment Period

The purpose of the Off-Treatment Period is to continue assessing patients for 12 weeks after patients have completed 100 weeks of study drug administration (or after the last dose of study drug if a patient discontinues study drug early). The Off-Treatment Period visits are of critical significance to this study. Every effort should be made to obtain off-treatment assessments following any discontinuation of study drug, whether at the planned Week 100 timepoint or at an earlier timepoint during the study.

For patients who remain on study drug through Week 100, the planned Off-Treatment Period begins the day after the Week 100 visit and continues through Week 112. Patients must complete 7 visits during the Off-Treatment Period, as listed in Table 4, and as described below:

- Week 103 visit (21 – 25 days from date of last dose)
- Week 104 A & B visits (28 – 36 days from date of last dose) at least one day apart
- Week 108 A & B visits (56 – 64 days from date of last dose) at least one day apart
- Week 112 A & B visits (84 – 92 days from date of last dose) at least one day apart

To the extent possible, sites should try to avoid bringing patients in very late in the window for a particular visit, and then very early in the window for the next timepoint. For example, a patient who completes Week 104 A & B visits 35 and 36 days after last dose, then completes Week 108 A & B visits 56 and 57 days after last dose, would have Week 104 and Week 108 visits spaced only 20 days apart, rather than ~4 weeks apart. Sites should attempt to achieve an approximate 4-week interval between Weeks 100, 104, 108, and 112.

For patients who discontinue study drug prior to Week 100, the patient should be assessed at the following timepoints, see Off Treatment Period in Table 4 for full list of assessments:

- An End of Treatment visit as close as possible to the last dose
- One visit 3 weeks after discontinuation (21 – 25 days from date of last dose)
- Two visits 4 weeks after discontinuation (28 – 36 days from date of last dose) at least one day apart
- Two visits 8 weeks after discontinuation (56 – 64 days from date of last dose) at least one day apart

- Two visits 12 weeks after discontinuation (84 – 92 days from date of last dose) at least one day apart

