#### **9.4. Treatment Compliance**

The investigator or his/her designated and qualified representatives will only dispense study drug to patients enrolled in the study in accordance with the protocol. Patients should administer study drug exactly as instructed by the site. Non-compliance is defined as taking less than 80% or more than 110% of expected study medication during any evaluation period (visit to visit). A lack of treatment compliance during any evaluation period (visit to visit) should be entered as a protocol deviation.

Patients should record in the patient diary all administered and missed doses of study drug. The reason for a missed dose should be recorded in the patient diary. Missing dose includes inadvertent missed doses as well as study drug interruptions and discontinuations. Patients will be asked to return all unused study drug (study drug bottles and any unused capsules). The study drug must not be used for reasons other than that described in the protocol.

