#### **10.4. Study Drug Administration**

Please refer to Section 9.10.13 for details on study drug administration. It is the responsibility of the investigator or designee to provide clear instructions to the patient regarding the number and type of capsules to be ingested at each study drug administration time point listed in Table 4. Patients must be instructed to continue taking study drug once daily through Week 100 unless: (1) the patient has been otherwise instructed by the investigator or (2) the patient has been formally discontinued from study treatment.

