4. STUDY DESIGN

4.1. Summary of Study Design

This international, multi-center, randomized, double-blind, placebo-controlled Phase 3 trial will study the safety, tolerability, and efficacy of bardoxolone methyl in qualified patients with ADPKD. Approximately 850 patients will be enrolled.

Patients will be randomized 1:1 to either bardoxolone methyl or placebo. Randomization will be stratified by eligibility eGFR category (30 to <60; ≥ 60 to 90), concomitant tolvaptan use (yes, no), and screening albumin to creatinine ratio (ACR; ≤ 300 mg/g, >300 mg/g). Patients randomized to placebo will remain on placebo throughout the study, undergoing sham titration. Patients with eGFR 60 to 90 mL/min/1.73 m² at screening should not comprise more than approximately 40% of enrolled patients.

The maximum bardoxolone methyl dose will be determined by baseline proteinuria status. Patients with baseline ACR ≤ 300 mg/g will be titrated to a maximum dose of 20 mg, and patients with baseline ACR >300 mg/g will be titrated to a maximum dose of 30 mg. Patients receiving bardoxolone methyl will start with once-daily dosing at 5 mg and will dose-escalate to 10 mg at Week 2, to 20 mg at Week 4, and then to 30 mg at Week 6 (only if baseline ACR >300 mg/g) unless contraindicated clinically and approved by the medical monitor. Dose de-escalation is permitted during the study if indicated clinically, and subsequent dose re-escalation is also permitted to meet the dosing objective of the highest tolerated dose.

[figure not shown]
All patients in the study will follow the same visit and assessment schedule. Following randomization on Day 1, patients will be scheduled to be assessed during treatment at Week 1, 2, 4, 6, 8, 12, 24, 36, 48, 52, 64, 76, 88, and 100 and by telephone contact on Day 3, 10, 21, 31, 38, and 45. Patients will continue study drug treatment through Week 100. Patients will also be scheduled to be assessed at an in-person follow-up visit at Weeks 103, 104, 108, and 112, after the end of treatment, respectively. The Data Monitoring Committee performs quarterly reviews of unblinded data for safety throughout the study.

Efficacy endpoints will be analyzed after all enrolled patients have completed the study and the final database lock.

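### SAP 9.2 leaves days with no dose due in the compliance denominator, so on the version 6+ schedule a fully adherent patient followed to Week 112 scores 92.6% after 100 weeks of dosing and 48.1% after 52

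*SAP*

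**What the plan says.** SAP Section 9.2 computes compliance as 100 times doses received (dispensed minus returned) over the patient's days in the study, "excluding the off-treatment periods between Week 48 to Week 52 prior to protocol version 6 and Week 100 to Week 104". The same section lists, among its summaries, the number of patients at 80% compliance or more through Week 100. It defines exposure on a different interval: last dose minus first dose plus one, less the Week 48–52 gap for patients before protocol version 6.

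On the schedule itself:

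- SAP Section 4.1: "Patients will continue study drug treatment through Week 100". Protocol Section 10.4 makes this a daily dose: "Patients must be instructed to continue taking study drug once daily through Week 100 unless" told otherwise by the investigator or formally discontinued.
- Protocol Section 8.3.3, for patients who stay on drug to Week 100: "the planned Off-Treatment Period begins the day after the Week 100 visit and continues through Week 112".
- Protocol Sections 8.3.3 and 8.5.1 ask patients who stop early to remain in follow-up through Week 112.
- Protocol Section 9.4 sets its own rule against what was due: "Non-compliance is defined as taking less than 80% or more than 110% of expected study medication during any evaluation period (visit to visit").

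**The concern.** The Week 100–104 exclusion fits a design with a four-week washout at the end. The current washout is twelve weeks, so for a patient who completes it, eight drug-free weeks (104 to 112) are scored as though doses had been missed. For an early stopper, every day in follow-up after the last dose, other than the excluded blocks, is scored the same way. A compliance percentage should show how much of the drug that was due was taken. Here it also moves with how long the patient was followed. The more fully a site meets the protocol's request to keep early stoppers in follow-up, the lower those patients score, and some who took every dose due will fall outside the 80% tally.

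**Working it through.** The documents give no worked compliance percentage, so there is no plan figure to reproduce first. The check applies the SAP formula to patients who take every dose that is due.

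**Inputs.** Week 52 = Day 364, Week 100 = Day 700, Week 104 = Day 728, Week 112 = Day 784 (SAP Table 4 targets). The last visit window closes at Day 792 (SAP Table 2). One dose a day. Excluded: 28 days for Weeks 100–104, and a further 28 for Weeks 48–52 if the patient was on the schedule before version 6.

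**Formula.** Score = 100 × doses received / (days in study − excluded days).

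| Patient, all due doses taken | Calculation | Score |
|---|---|---|
| Version 6+, completes Week 100, followed to Day 784 | 700 / (784 − 28) = 700/756 | 92.6% |
| Version 6+, stops at Week 76, followed to Day 784 | 532/756 | 70.4% |
| Version 6+, stops at Week 52, followed to Day 784 | 364/756 | 48.1% |
| Version 6+, completes Week 100, followed to Day 792 | 700 / (792 − 28) = 700/764 | 91.6% |
| Version 6+, stops at Week 52, followed to Day 792 | 364/764 | 47.6% |
| Version 6+, stops at Week 52, leaves 12 weeks later | 364 / (364 + 84) = 364/448 | 81% |
| Week 48–52 gap, dosed to Week 100, followed to Day 784 | (700 − 28) / (784 − 56) = 672/728 | 92.3% |
| Week 48–52 gap, last dose at Week 48, followed to Day 784 | 336/728 | 46.2% |
| Earlier design, finished at Week 104 | 672 / (728 − 56) = 672/672 | 100% |

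**Capped at Week 100.** If the through-Week-100 wording ends the denominator at Day 700, the version 6+ completer scores 700/700 = 100%. The Week 52 stopper followed to Week 100 scores 364/700 = 52%.

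**First dose to last dose.** The completer scores 700/700 and the Week 52 stopper 364/364, both 100%.

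**Programme termination.** The SAP introduction says sites were told on 10 May 2023 that development had stopped. The documents do not say how long patients were followed after that, so this is an assumption with a range. A patient with d dosing days who stops then, and leaves before Week 100, scores d/(d + 84) with 12 weeks of further follow-up, or d/(d + 28) with 4 weeks. The 80% mark falls at d = 336 (336/420) and d = 112 (112/140) respectively. Fully adherent patients with fewer dosing days than that would score below 80%.

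**The case against.** The strongest reply concerns early stoppers. Protocol Section 9.4 lists discontinuations alongside interruptions among missing doses, so scoring a stopper against the planned course could be a deliberate definition rather than an error. The 80%/110% rule there is also a visit-to-visit deviation trigger, not the SAP's overall summary, and the SAP governs where the two differ. Part of this stands: adherence to the planned course is a legitimate quantity. But the line on discontinuations says what the diary should record, and it cannot justify counting Weeks 104–112, when no patient is due a dose. Nor does the formula measure the planned course, since its denominator varies with each patient's follow-up: the same dosing record gives 48.1% or 81%.

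Second, the through-Week-100 wording may cap the denominator. That would repair the completer's score but not the stopper's, and it would make the Week 100–104 exclusion unnecessary, so the two parts of the section still need reconciling.

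Third, the Week 100–104 exclusion is not merely a leftover. Patients who finished at Week 104 under the earlier design need it and are scored correctly.

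A reader might infer from 0.8 × 756 = 604.8 that no patient can reach 80% with fewer than 605 days of dosing. The documents do not support that. The denominator is each patient's own time in the study, and a Week 52 stopper who leaves 12 weeks later passes at 81%. A reader might also infer that the arms will appear to differ in compliance. That would require unequal early stopping or follow-up, for which the documents give no figures.

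**Conclusion.** The point holds as a defect in a descriptive summary. As written, the formula counts days with no dose due as missed doses. For a version 6+ patient followed to Day 784 it costs a perfect completer about 7 percentage points, which does not take that patient below 80%. It gives a perfect complier who stopped at Week 52 a score of 48.1%. These figures rest on one dose a day, every due dose taken, and follow-up to Week 112; shorter follow-up raises the early stopper's score. The early-stopper problem survives either reading of the through-Week-100 wording, while the completer problem arises only if Week 100 is not a cap.

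It would be wrong to carry this over to the efficacy results. SAP Section 6.3 defines only ITT and Safety populations, neither based on compliance, and compliance enters neither the Week 108 ANCOVA nor the Week 100 MMRM. Disposition, reasons for stopping and exposure duration are tabulated separately, so a careful reader could see the early stopping behind a low score.

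**What to change.** Replace the denominator in SAP Section 9.2 with date of last dose minus date of first dose plus one, less the Week 48–52 off-treatment days for patients before protocol version 6. The section already uses this interval for exposure. Temporary interruptions between first and last dose would still count as missed, in line with Protocol Section 9.4.

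At minimum, exclude all days after the last dose, including the whole of Weeks 100–112, and say how that fits with a tally of patients at 80% or more through Week 100.

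The cost is one sentence, with no new data, and it should be settled before database lock. The downside is small: early stopping would no longer lower the compliance figure, and someone who stopped after one dose would score 100%. That information is already carried by the disposition table and the exposure-duration categories. If the sponsor also wants adherence to the planned 100-week course, it should be a separate, labelled summary.
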